10.1.2 Total Exposure to Pimavanserin across Double-blind and Open-label Periods

For subjects who received pimavanserin in double-blind Study ACP-103-032, the total duration of exposure (in days) to pimavanserin will be calculated as the sum of the exposure durations in the double-blind and open-label periods. The cumulative dose of pimavanserin will be calculated by first multiplying the number of doses taken by the dose level (in mg) for each kit returned to the site during both the double-blind and the open-label study periods and then summing the results for all kits. The average daily dose of pimavanserin (in mg) will be calculated as the cumulative dose (in mg) divided by total duration of exposure (in days).

For subjects who received placebo in double-blind Study ACP-103-032, the total duration of exposure (in days) to pimavanserin, the cumulative dose of pimavanserin, and the average daily dose of pimavanserin across the double-blind and open-label periods will be the same as the values calculated for the open-label study period alone. Duration of exposure, cumulative dose, and average daily dose for pimavanserin across the double-blind and open-label periods will be summarized descriptively.

Duration of total exposure will be summarized as both continuous and categorical variables. For categorical presentation, the number and percentage of subjects in each of the following categories will be presented: <4 weeks (1 to 27 days), 4 to <8 weeks (28 days to 55 days), 8 to <12 weeks (56 days to 83 days), 12 to <16 weeks (84 days to 111 days), 16 to <28 weeks

(112 days to 195 days), 28 to <40 weeks (196 days to 279 days), 40 to <52 weeks (280 days to 363 days) , 52 to <64 weeks (364 days to 447 days), and ≥ 64 weeks (448 days or longer).

In addition, summaries of whether subjects had any dose change (yes vs. no), their highest dose level (20 mg or 34 mg) and their last dose level (20 mg or 34 mg) will also be provided.

10.2 Measurement of Treatment Compliance

Study drug dosing compliance (in percentage) during the open-label study period for a subject is defined as:

$$\frac{(\text{total number of tablets actually taken})}{(\text{total number of tablets expected to be taken})} \times 100$$

With the total number of tablets actually taken calculated as:

$$(\text{the total number of tablets dispensed}) - (\text{the total number of tablets returned})$$

The number of tablets expected to be taken is calculated as:

$$(\text{the duration of exposure}) \times 2.$$

The duration is multiplied by 2 because the subject is instructed to take 2 tablets per day.

Compliance will be summarized as both continuous and categorical variables. For categorical presentation, the number and percentage of subjects in each of the following categories will be presented: <80%, 80 to 120%, and >120%.

11 CONCOMITANT AND POST-TREATMENT MEDICATION

Concomitant medication is defined as any medication with a start date prior to the first dose of the open-label study drug and continuing after the first dose of the open-label study drug or with a start date between the first dose of the open-label study drug and last dose of open-label study drug, inclusive. Any medication with a start date after the date of the last dose of open-label study drug will be considered as post-treatment medication. Concomitant and post-treatment medications will be summarized separately.

Medications will be coded using WHO Drug Dictionary (WHODD) 2016 March or newer version. The number and percentage of subjects taking each drug class (ATC Level 3) and medication preferred term will be tabulated for the Safety Analysis Set. Multiple medication usage by a subject in the same ATC category will be counted only once.

12 EFFICACY ANALYSES

All efficacy summaries will be performed for the Safety Analysis Set. No hypothesis testing is planned. Descriptive summaries of all efficacy endpoints will be provided.

12.1 Exploratory Efficacy Variables

The exploratory efficacy endpoints include the following:

- Change from Baseline in Cohen-Mansfield Agitation Inventory (CMAI) total score
- Change from Baseline in Zarit Burden Interview (ZBI) total score
- Modified Alzheimer's Disease Cooperative Study - Clinical Global Impression of Change (mADCS-CGIC) agitation score
- Change from Baseline in Neuropsychiatric Inventory-Clinician Rating Scale (NPI-C) combined agitation and aggression domain scores
- Change from Baseline in NPI-C total score
- Change from Baseline in NPI-C individual domain scores
- Change from Baseline in Mini-Mental State Examination (MMSE) score
- Change from Baseline in Karolinska Sleepiness Scale (KSS) score
- Change from Baseline in CMAI subscale scores
- Change from Baseline in Alzheimer's Disease Cooperative Study - Activities of Daily Living Inventory (ADCS-ADL) score

12.2 Adjustment for Covariates

Not applicable.

12.3 Handling of Missing Data

Any derived scores (i.e. total, domain or subscale scores) that are missing after any imputation of individual missing items as described in [Section 5.2](#) will not be imputed.

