4.2 Subject Withdrawal

In accordance with the Declaration of Helsinki and other applicable regulations, a subject has the right to withdraw from the study at any time, and for any reason, without prejudice to his or her future medical care.

If consent has been given by a LAR because the subject is not competent to provide informed consent, the LAR has the right to withdraw the subject from the study at any time, and for any reason, without prejudice to the subject's future medical care or any penalty or loss of benefits to the LAR.

The study partner/caregiver has the right to withdraw his or her agreement to participate in the study at any time, and for any reason, without prejudice to the subject's future medical care or any penalty or loss of benefits to the caregiver. If the study partner/caregiver withdraws agreement to participate, the subject must be discontinued unless another suitable study partner/caregiver is available to sign the agreement to participate.

Subjects may be discontinued or withdrawn from the study for a number of reasons, including but not limited to those listed below:

- Adverse events(s) (serious or non-serious)
- The Investigator becomes aware of an impending and unexpected change in the subject's living situation (e.g., change in caregiver, change in facility, moving from home to facility, moving from one family member or caregiver's home to another) that s/he judges may cause a major disruption in the subject's behavior
- The Investigator determines that continuation in the study would be detrimental to a subject's well-being
- At the discretion of the Sponsor
- Subject fails to comply with protocol requirements
- Voluntary withdrawal of consent by subject or subject's LAR (wherever possible, the reason for withdrawal of consent should be collected)
- Subject is lost to follow-up
- Female subject becomes pregnant

Every effort should be made to complete the end of study (EOS)/early termination (ET) visit should a subject discontinue prematurely from the study.

If a subject is lost to follow-up, every effort should be made to phone the subject's caregiver approximately 30 days after last known contact with the subject in order to assess the subject's current status. All phone contact with the caregiver should be documented.

For subjects who continue to be followed for safety, SAEs should continue to be reported as described in [Section 7.5.1](#).

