5.6 Concomitant Medications

All ongoing concomitant medications will be captured from the preceding double-blind study (ACP-103-032) and will be recorded from Baseline through the EOS/ET visit.

In order to ensure that appropriate concomitant therapy is administered, it is essential that subjects be instructed not to take any medication without prior consultation with the Investigator.

The Investigator may prescribe, adjust, or discontinue appropriate medication to treat or manage AEs. The Sponsor and Investigator will confer to determine whether it is appropriate to continue such a subject in the trial if a prohibited medication is prescribed.

Subjects who take prohibited concomitant medications during the trial will be discontinued, unless the discontinuation presents an unacceptable medical risk. The justification to allow the subject to continue in the trial will be made by the Sponsor with medical input from the Investigator, and will be documented. If allowed to remain in the trial, this will be reported as a major protocol deviation and not a waiver. All follow-up safety assessments must be completed and documented as outlined in the protocol.

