9.3 Handling of Dropouts and Missing Data

Handling of missing values will be described in detail in the SAP. For responder analyses, two sets of summaries will be provided, one based on observed cases and the other counting subjects with missing values as non-responders.

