2.2 Exploratory Objectives and Endpoints

2.2.1 Exploratory Objectives

To evaluate the persistence of the effects of pimavanserin treatment on:

- Agitation and aggression
- Caregiver burden
- The clinician's global assessment of treatment benefit
- Other neuropsychiatric symptoms
- Cognition

- Functional status
- Sleep and daytime wakefulness

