5.2.1 Cohen-Mansfield Agitation Inventory Long-form (CMAI)

The CMAI is assessed at Baseline, and Weeks 2, 4, 8, 12, 20, 28, 36, 44, and 52/ET visits.

The CMAI is a 29-item scale designed to systematically assess agitation, rated on a 7-point (1-7) scale of frequency (1 = Never; 2 = Less than once a week; 3 = Once or twice a week; 4 = Several times a week; 5 = Once or twice a day; 6 = Several times a day; 7 = Several times an hour). Subjects are rated by their primary caregiver regarding the frequency with which they manifest physically aggressive, physically non-aggressive, and verbally agitated behaviors. The CMAI in this study is to be completed by interview of the caregiver. Ratings are inclusive of the 2 or 4 weeks prior to the administration of the scale.

In addition to the 7-point frequency scale, there are two other options for rating the behavior: 1) “8 - would occur if not prevented” (e.g., a person is physically restrained so he/she cannot pace), and 2) “9 - not applicable” (e.g., a non-verbal resident not being able to repeat sentences or questions, or a person who cannot walk or move a wheelchair not being able to pace, an amputated person not being able to kick). These two ratings are used only if the

behavior really has never occurred in the past two weeks. If it has occurred, then the 1-7 point frequency scale should be used. These ratings of 8 and 9 are not included in the CMAI total score calculation. The CMAI has a range of 29-203 points, with higher scores indicating more severe agitation symptoms. If there are less than 6 missing items then the total score will be imputed by replacing each missing item with the mean (rounded to the nearest integer) of the non-missing values for that subject and timepoint. If there are more than 5 missing items then the total score will be missing.

In addition to the total score, behavioral subscales will be defined as follows ([Rabinowitz et al, 2005](#)):

- Aggressive Behavior: 12 Items (minimum = 12, maximum = 84)
- Sum of scores from items 3, 4, 7, 8, 9, 10, 11, 13, 14, 15, 21 and 25
- Physically Non-aggressive Behavior: 6 Items (minimum = 6, maximum = 42)
- Sum of scores from items 1, 2, 16, 22, 26, and 29
- Verbally Agitated Behavior: 4 Items (minimum = 4, maximum = 28)
Sum of scores from items 5, 6, 18, and 19
- Hiding and Hoarding : 2 Items (minimum = 2, maximum =14)
Sum of score from items 23 and 24

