13 METHODS OF EFFICACY ANALYSES

13.1 Exploratory Efficacy Analyses

Descriptive statistics for all exploratory efficacy endpoints listed in [Section 12.1](#) will be tabulated by double-blind treatment group at each scheduled timepoint. The summaries of the change from Baseline results will be presented in two ways as specified in [Section 5.1](#), by double-blind treatment group at each scheduled timepoint.

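### Mean changes on the continuous efficacy scales are observed-case only, with no sensitivity analysis for missed visits; if leavers are worse than stayers, late-visit means may overstate persistence of effect

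*SAP*

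**What the plan says.** Protocol 9.3 defers the matter: "Handling of missing values will be described in detail in the SAP". It fixes one thing itself, that responder analyses come in two sets, "one based on observed cases and the other counting subjects with missing values as non-responders".

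The SAP then works at two levels.

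- **Items.** Section 5.2 fills gaps within a completed assessment. For the CMAI total: "If there are less than 6 missing items then the total score will be imputed by replacing each missing item with the mean" of that subject's other items at the same timepoint. This does nothing for a missed visit.
- **Visits.** SAP 12.3 does not impute "Any derived scores (i.e. total, domain or subscale scores) that are missing after any imputation of individual missing items". SAP 13.1 plans "Descriptive statistics for all exploratory efficacy endpoints listed in" SAP 12.1, by double-blind treatment group and scheduled timepoint. SAP 12.2 has no covariate adjustment, and no model appears anywhere.

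SAP 5.3.1 makes early-termination (ET) assessments eligible for the by-visit summaries. Under SAP 5.3.2, the assessment closest to the target day is used when several fall in one window. SAP 13.1.1 applies missing = non-response to CMAI total, NPI-C agitation and aggression (combined and individual) and mADCS-CGIC.

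The objective these tables serve (SAP 2.2.1) is "To evaluate the persistence of the effects of pimavanserin treatment on" agitation and aggression, caregiver burden, cognition, function and other outcomes.

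**The concern.** A visit mean over 52 weeks answers a question about persistence only if the subjects still contributing at Week 52 resemble those who started. A flat observed-case curve can arise because the effect lasts, or because subjects who worsened have left. Mean changes alone cannot separate the two.

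The protocol gives some reason to expect that leaving is related to agitation:

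- Appendix B prohibits all antipsychotics, and Protocol 5.6 states: "Subjects who take prohibited concomitant medications during the trial will be discontinued, unless the discontinuation presents an unacceptable medical risk". Protocol Section 1 itself describes frequent off-label antipsychotic use for these symptoms.
- Protocol 4.2 lists a disruptive change in living situation, including a move into a facility, as a reason for withdrawal. Section 1 names neuropsychiatric symptoms as a leading cause of nursing home placement.
- Protocol 4.2 also lists Investigator-judged detriment to well-being.

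The plan allows for missing visits in the responder analyses but not in the means, which make up most of the exploratory list.

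**Working it through.** The documents state no dropout rate, SD, effect size or bias figure for this point, so there is nothing to reproduce. The only relevant number is the enrolment of up to about 111 (SAP 3.5). All other inputs below are assumptions.

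**1. Size of the bias.** Let m be the share with no score at Week 52, S the mean change in those observed, L the mean change the others would have shown, and d = L - S. On the CMAI a higher score is worse, so d > 0 means leavers are worse.

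- Mean over everyone = (1 - m) × S + m × L = S + m × d
- Observed-case mean = S
- Overstatement of improvement = m × d

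| m | n observed of 111 | d = -5 | d = 0 | d = 5 | d = 15 |
|---|---|---|---|---|---|
| 20% | 89 | -1.0 | 0 | 1.0 | 3.0 |
| 30% | 78 | -1.5 | 0 | 1.5 | 4.5 |
| 35% | 72 | -1.75 | 0 | 1.75 | 5.25 |
| 50% | 56 | -2.5 | 0 | 2.5 | 7.5 |

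For 30-50% missing and a 5-15 point gap, the range runs from 0.30 × 5 = 1.5 to 0.50 × 15 = 7.5 points. Negative entries mean that improvement is understated.

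**2. Selection simulation.** Week 52 changes were drawn with assumed mean -10 and SD 20, and the log-odds of dropout were tied to the score.

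- Dropout unrelated to score: bias about 0.
- Log-odds rising by 0.5 to 1.0 per SD of worse score: improvement overstated by 1.9-3.5 points (20% missing), 3.3-5.8 (35%) and 4.7-8.2 (50%).
- The reverse relation at 0.5 per SD: improvement understated by 1.9, 3.3 and 4.7 points.

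**3. How far ET scores help.** By SAP Table 4 the Week 12 window is Days 71 to 112, with target Day 85. Take a Week 12 visit on Day 85 and an ET visit on Day 100. Both fall in the window, at 0 and 15 days from target, so the ET score is not used in the means. An ET visit on Day 120 falls in the Week 20 window (Days 113 to 168) and can count there, but not later. An ET score reaches the Week 52 mean only if taken on Days 337 to 379.

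**4. How far the responder summaries help.** When missing counts as non-response, rate = observed-case rate × (1 - m). An observed rate of 50% becomes 0.50 × 0.80 = 40%, 0.50 × 0.65 = 32.5% or 0.50 × 0.50 = 25%. It falls by this amount whoever leaves, so it gives a floor and does not show whether leavers were worse. ZBI, MMSE, KSS, ADCS-ADL, NPI-C total, the other 12 of the 14 NPI-C domains and the CMAI subscales have no such companion.

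**The case against.** A reader might infer that the protocol withdraws subjects whose agitation relapses, so that late means are conditional on not having relapsed. The documents do not say this. Protocol 4.2 is open and permissive ("Subjects may be discontinued or withdrawn from the study for a number of reasons, including but not limited to those listed below"), and its list names neither relapse nor lack of efficacy. Recurrent agitation can be handled within the study by dose adjustment (5.4) or rescue benzodiazepine (5.6.3), and those subjects stay in the means. The antipsychotic route is an inference in two steps, and the rule has a medical-risk exception. This part of the objection stands in full.

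It is also fair that the direction of bias is not established. Exit for an adverse event, withdrawal of consent or loss to follow-up need not track agitation. With d = 0 there is no bias.

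The planned outputs are not blind to attrition. They give n with every mean (SAP 5.1), discontinuations by reason (SAP 6), Kaplan-Meier curves of time on drug (SAP 10.1.1), ET scores in their own windows, and the non-response summaries. Together these show how many leave and why. They do not link leaving to the scores, and for ZBI there is no companion analysis at all. So the mitigation is real but partial.

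Finally, the endpoints are exploratory, the study is open-label and uncontrolled, and no testing is planned. No model can separate drug effect from natural course here. That limits the weight of the point but does not remove it, because the tables will still be read as evidence on persistence.

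**Conclusion.** The point holds in conditional form. Mean changes are observed-case only, no sensitivity analysis for missed visits is planned, and the protocol contains routes by which worsening agitation can lead to exit. If leavers are worse than stayers, late-visit means may overstate persistence, by 1.5 to 7.5 CMAI points under the assumed 30-50% missing and 5-15 point gap. The stronger conclusion, that these means do overstate persistence, is not supported: both sign and size depend on a dropout pattern that the documents do not describe. This is a cheap improvement to an exploratory analysis. It does not touch the primary safety endpoint.

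**What to change.** In SAP 12.3 and 13.1, keep the observed-case tables. For CMAI total, NPI-C combined agitation and aggression, and ZBI, add:

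- **(a)** visit means with 95% CIs from a likelihood-based repeated-measures model with Study 032 group, visit, group-by-visit and Baseline, and no tests. State that it relies on missing at random. CMAI and ZBI have 9 post-Baseline visits, so an unstructured covariance needs 9 × 10 / 2 = 45 parameters from about 111 subjects; name a simpler fallback structure in advance.
- **(b)** observed visit means shown separately for Week 52 completers and for subjects who discontinued, including the latter's ET score even where SAP 5.3.2 would pass it over.

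Display (b) shows directly whether leavers were worsening. Estimate (a) uses their earlier scores but does not protect against dropout driven by unobserved worsening. A last-value end-of-treatment row is not recommended, since it brings debatable assumptions of its own.

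The cost is some SAP wording and a few tables from data already collected. The downside for the sponsor is that late-visit means may look less favourable. The report should say that neither addition separates drug effect from natural course.

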12.4 Multiple Comparisons / Multiplicity

No hypothesis testing is planned.

12.5 Examination of Subgroups

Subgroup analyses by geographic region (North America, Europe, or Rest of World) will be performed for the change from Baseline in the CMAI total score and the ZBI total score.

13 METHODS OF EFFICACY ANALYSES

13.1 Exploratory Efficacy Analyses

Descriptive statistics for all exploratory efficacy endpoints listed in [Section 12.1](#) will be tabulated by double-blind treatment group at each scheduled timepoint. The summaries of the change from Baseline results will be presented in two ways as specified in [Section 5.1](#), by double-blind treatment group at each scheduled timepoint.

13.1.1 Responder Analyses

In the responder analyses, since CMAI is an interval scale that lacks a natural zero point (1 = Never), the percent change in CMAI total score will be calculated based on corrected scores after subtracting 29 points from the raw scores. For example, if a subject's Baseline CMAI total score is 79 and Week 8 CMAI total score is 29 (absent of all agitation behaviors), the percent change from Baseline to Week 8 in CMAI total score will be calculated as $[(29 - 29) - (79 - 29)] \div (79 - 29) \times 100\% = -100\%$.

Multiple types of responders will be summarized at each scheduled post-Baseline visit:

- $\geq 20\%$, $\geq 30\%$, $\geq 50\%$, $\geq 75\%$ and 100% reduction in the CMAI total score from Baseline
- $\geq 20\%$, $\geq 30\%$, $\geq 50\%$, $\geq 75\%$ and 100% reduction in NPI-C combined agitation and aggression domain scores from Baseline
- $\geq 20\%$, $\geq 30\%$, $\geq 50\%$, $\geq 75\%$ and 100% reduction in the individual agitation and aggression NPI-C domain scores from Baseline
- mADCS-CGIC score of 1 (marked improvement) or 2 (moderate improvement)

Other responder criteria based on point changes may be included based on examination of cumulative distribution functions and anchoring to the ADCS-CGIC.

For each of these responder analyses, the proportion of responders will be summarized by double-blind treatment group at each timepoint using observed cases and also with missing values imputed as non-response.

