5.1 General Data Reporting Conventions

For continuous variables, the following summary statistics will be provided: number of subjects, mean, standard error of the mean (SE), standard deviation (SD), minimum, maximum and median. Unless specified otherwise, means, medians, and confidence intervals (CIs) will be presented to one more decimal place than the raw data, and the SDs deviations and SEs will be presented to 2 more decimal places than the raw data. Unless specified otherwise, all confidence intervals will be 2-sided 95% confidence intervals.

For categorical variables, summaries will include the number and percentage of subjects in each category, using the number of subjects with non-missing values as the denominator for the percentages (unless otherwise specified). Categories with zero counts will not have zero percentages displayed. Percentages will be presented with 1 decimal place.

When converting number of days to months, it will be calculated by dividing the number of days by 365.25 and then multiplying by 12. When converting number of days to years, the number of days will be divided by 365.25.

No hypothesis testing is planned. Descriptive summaries of all safety and efficacy endpoints will be provided. All safety and efficacy measures will be summarized for the Safety Analysis Set. Summaries by treatment group according to the original treatment in double-blind Study ACP-103-032 (placebo, pimavanserin 20 mg, and pimavanserin 34 mg) will be provided. All references to double-blind treatment group refer to the initial treatment group in Study ACP-103-032.

For each continuous measure in safety and efficacy analyses, change from Baseline results will be presented in two ways:

1. Using the Baseline from Study ACP-103-033 and reporting the changes across Study ACP-103-033 timepoints;
2. Using the Baseline from Study ACP-103-032 and reporting the changes across the timepoints of both the double-blind Study ACP-103-032 and the open-label Study ACP-103-033.

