5.2 Derived Variables

In general, assessment total scores and subscale scores will be derived within the analysis datasets. In the event that total scores and/or subscale scores are also collected on the electronic case report form (eCRF), the derived values will be used for all summaries. Both the raw and derived scores will be presented in listings.

All Baseline assessments that are referred to in the following sections will be carried over from the Week 12 visit of double-blind Study ACP-103-032, where applicable.

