5.3 Analysis Visit Windows

In general, the open-label Baseline assessment will be defined as the last non-missing assessment, including those from repeated and unscheduled measurements, before or on the first open-label dose date. Exceptions to this definition will be handled on a case by case basis.

Efficacy and safety assessments will be summarized by analysis visit as presented in Table 4 below.

Table 4 Analysis Visit Windows

Open-label (OL) Analysis Visit Name	Target Study Day¹	Study Day Interval
OL Baseline	1	≤1(based on the first open-label dose date)
OL Week 2	15	2 to 21
OL Week 4	29	22 to 42
OL Week 8	57	43 to 70
OL Week 12	85	71 to 112

OL Week 20	141	113 to 168
OL Week 28	197	169 to 224
OL Week 36	253	225 to 280
OL Week 44	309	281 to 336
OL Week 52	365	337 to 379
OL Follow-up	395	380 – maximum

¹ If the assessment date \geq first open-label dose date, study day = assessment date – first open-label dose date + 1; otherwise study day = assessment date – first open-label dose date. Study day 1 is the first open-label dose date.

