8 DEMOGRAPHICS AND OTHER BASELINE CHARACTERISTICS

Demographics and open-label Baseline characteristics will be summarized for Safety Analysis Set using descriptive statistics. Summaries by region will also be presented. Variables include age, sex, race, ethnicity, height, weight, body mass index (BMI), region, Baseline living situation category, Baseline caregiver category, Baseline NPI-C combined agitation and aggression domain score, Baseline MMSE total score, Baseline CMAI total score, Baseline ZBI total score, and concomitant selective serotonin reuptake inhibitor (SSRI) usage (yes/no).

Age (the reported age reflects a subject’s age at the open-label Baseline visit date), Baseline CMAI total score, Baseline MMSE total score, and Baseline NPI-C combined agitation and aggression domain score will be presented as both continuous and categorical variables. Age will be presented as ≤ 85 and > 85 years old. Category of Baseline CMAI will be presented as < 65 and ≥ 65 . Category of Baseline NPI-C combined agitation and aggression will be

presented as <22 and ≥ 22 . Category of Baseline MMSE will be presented as ≤ 10 , 11-20 and >20 .

Alzheimer's disease history will be summarized for Safety Analysis Set using descriptive statistics. Variables include:

- Time (year) since diagnosis of probable Alzheimer's disease
- Duration (year) of symptoms of Alzheimer's disease
- Duration (year) of symptoms of agitation/aggression

Baseline visit date will be used as the reference date for calculating the durations listed above.

A listing of living situation and caregiver information by subject and visit will also be provided.

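### Does it matter that SAP 13.1.1 names no study for the Baseline behind the CMAI and NPI-C responders?

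*SAP*

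**What the plan says.** SAP 13.1.1 defines CMAI responders by reductions of at least 20, 30, 50 and 75 percent "and 100% reduction in the CMAI total score from Baseline". It uses the same cut-offs for the NPI-C combined agitation and aggression score and for the two domains separately. Percent change in CMAI is taken after subtracting 29 from each score. Neither the definition nor its worked example names a study.

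Other text bears on the meaning of Baseline:

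- SAP 5.2 says Baseline assessments "will be carried over from the Week 12 visit of double-blind Study ACP-103-032, where applicable".
- SAP 5.3 defines one Baseline only: "the open-label Baseline assessment will be defined as the last non-missing assessment", up to the first open-label dose.
- SAP 8 opens with "Demographics and open-label Baseline characteristics will be summarized for Safety Analysis Set" and then uses the bare word for the same thing: "Category of Baseline CMAI will be presented as" below 65 or at least 65.
- SAP 5.1 states: "For each continuous measure in safety and efficacy analyses, change from Baseline results will be presented in two ways", once from the 033 Baseline and once from the 032 Baseline.
- SAP 13.1, the parent heading of 13.1.1, repeats the rule for efficacy: "The summaries of the change from Baseline results will be presented in two ways as specified in" section 5.1.
- Protocol 9.6 says the CMAI and NPI-C responder definitions will match those of the parent study.
- Protocol 9.3 says of responder analyses that "two sets of summaries will be provided, one based on observed cases and the other counting subjects with missing values as non-responders".
- SAP 1 places table specifications in a separate document.

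**The concern.** The trial has two Baselines twelve weeks apart, and the exploratory objective is persistence of effect. If responders were counted only from the 033 Baseline, a subject who improved on pimavanserin in the parent study and held that gain would show no reduction and meet none of the percent criteria. The table would then describe further change after Week 12. It would also sit beside an mADCS-CGIC responder that SAP 5.2.5 ties to the parent Baseline, so one list would mix anchors.

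Several passages lean towards Week 12 as the default meaning of Baseline. The two-Baseline rule is worded for continuous measures and change summaries, whereas a responder proportion is categorical. Where the versions of the responder tables are listed, they differ by missing-data handling and not by Baseline.

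A related gap concerns subjects at the bottom of the scale at the anchor (CMAI 29, or NPI-C 0). Their percent change has a zero denominator, and the SAP does not say how they are classified.

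**Working it through.** **The plan's own figure.** Percent change = [(visit − 29) − (Baseline − 29)] ÷ (Baseline − 29) × 100. The SAP example, 79 falling to 29, gives (0 − 50) ÷ 50 = −100%, as stated.

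**Effect of the anchor on one subject.** Apart from 79, the scores are illustrative.

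| 032 Baseline / Week 12 / Week 52 (raw) | Less 29 | Change from 032 | Change from Week 12 |
|---|---|---|---|
| 79 / 49 / 49 | 50 / 20 / 20 | (20 − 50)/50 = −60% | (20 − 20)/20 = 0% |
| 79 / 79 / 54 | 50 / 50 / 25 | −50% | −50% |
| 79 / 89 / 59 | 50 / 60 / 30 | −40% | −50% |
| 79 / 29 / 29 | 50 / 0 / 0 | −100% | 0/0, undefined |

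In general, let B be the corrected 032 score, W the corrected Week 12 score and T the threshold. A later corrected score V qualifies from 032 if V ≤ B(1 − T), and from Week 12 if V ≤ W(1 − T). The anchors disagree only between those two limits. For B = 50 and W = 20, the highest qualifying raw scores are:

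| T | from 032 | from Week 12 | anchors disagree |
|---|---|---|---|
| 20% | 69 | 45 | 46–69 |
| 30% | 64 | 43 | 44–64 |
| 50% | 54 | 39 | 40–54 |
| 75% | 41 | 34 | 35–41 |
| 100% | 29 | 29 | none |

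The direction is not fixed. A subject who worsened in the parent study (third row of the first table) is a 50% responder only on the Week 12 anchor.

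**Which anchor the text supports.**

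1. Section 13.1.1 is a subsection of 13.1. CMAI and NPI-C scores are continuous measures, and 13.1.1 works from their percent change from Baseline. The natural reading is that it inherits the two-Baseline presentation of 13.1 and 5.1.
2. Protocol 9.6 imports the parent study's definitions. A 12-week study would not define response as reduction from its own Week 12 visit, so this favours the 032 anchor. It is not conclusive, because a definition could mean the cut-offs alone.
3. The SAP 5.2 sentence repeats the protocol's section 6.1 text on which data are carried over, and it is qualified. It is not clearly a rule for choosing an analysis anchor.
4. Protocol 9.3 is about dropouts and missing data. Naming two missing-data versions there does not exclude two Baselines.

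**Scale floor.** If k floor subjects in a group of N are counted as non-responders, a rate p among the others becomes p(N − k)/N. Assume 111 subjects split equally (N = 37) and p = 40%:

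- k = 1: 40 × 36/37 = 38.9%
- k = 2: 40 × 35/37 = 37.8%
- k = 4: 40 × 33/37 = 35.7%

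The loss is 1.1 to 4.3 points for k = 1 to 4. It is 0.7 points for N = 55 with k = 1, and 5.7 points for N = 28 with k = 4. N, p and k are all assumptions.

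**The case for a change.** The best case for a change is that two competent programmers could build different tables and both comply, and that one or two sentences would prevent it. SAP 14 restates the two-way rule for safety measures, and 13.1.1 does not. The choice matters most for the stated objective: in a table anchored only at Week 12, a previously treated subject who kept a response and one who lost it can both appear as non-responders.

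The wording gap and the arithmetic stand. The consequence is narrower. For former-placebo subjects the 033 Baseline precedes their first pimavanserin dose, so tables on that anchor do show open-label response and how long it lasts. The loss falls mainly on former-pimavanserin subjects, and only if the analysts ignore the parent heading and protocol 9.6.

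The floor gap also stands, and it arises on either anchor, since a single NPI-C domain can be 0 at either Baseline. But the obvious repair, exempting every floor subject from non-response, would be unsound. A subject at 29 at Week 12 who later relapses has plainly had no reduction, and exempting that subject would hide loss of response. Reporting how many start at the floor, split into those who stay there and those who worsen, is descriptive detail that suits the table specifications.

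**Conclusion.** No change to the plan follows. This is missing detail that analysts would probably fill sensibly. Nothing in SAP 13.1.1 prescribes a Week-12-only anchor, and the section structure together with protocol 9.6 points towards including the 032 Baseline.

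For an individual the effect can be large (−60% against 0%). For the study it is bounded: the tables are exploratory and descriptive, and no hypothesis is tested. Mean changes from the 032 Baseline are planned for the same scales, and the mADCS-CGIC responder is rated against the parent Baseline whatever anchor the other responders use.

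This rests on reading 13.1.1 as governed by its parent section, and on table specifications that are not among the documents. If those specifications showed only the 033 anchor, the CMAI and NPI-C responder tables should not be read as evidence on persistence in former-pimavanserin subjects. The numbers of subjects at the floor, and of those classified differently by the two anchors, cannot be derived from the documents.
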